1.4 Rationale

Novel strategies to enhance the antitumor activity of immune-checkpoint inhibitors are under development. This study will assess the immunomodulatory activity of entinostat in patients who have progressed while receiving the immune-checkpoint inhibitors nivolumab and ipilimumab or nivolumab alone. The overall hypothesis is that entinostat will restore the immune response and antitumor effect induced by the PD1/CTLA inhibition by suppressing Treg and MDSC function. The schedule of entinostat is based on our previous experience with this agent. Based on our working hypothesis that low dose HDAC inhibitors will have a suppressive function on Tregs and MDSC but not on T effector cells, the starting dose of entinostat will be 5 mg weekly.

2. STUDY OBJECTIVES AND ENDPOINTS

2.1 Objectives

2.1.1 Primary Objectives

Establish the recommended Phase II dose (RP2D) during the Safety Lead-In and to assess efficacy via objective response rate (ORR) via RECIST 1.1 during the Phase II study of entinostat in combination with nivolumab and ipilimumab in subjects with metastatic RCC who have progressed on nivolumab + ipilimumab regimen.

2.1.2 Secondary Objectives

- Characterize safety of entinostat in combination with nivolumab and ipilimumab
- Estimate ORR via Immune Related Response Criteria (irRC)
- Estimate progression free survival (PFS) via RECIST 1.1 and irRC
- Estimate overall survival (OS)

2.1.3 Correlative Objectives

Characterize PD-L1/2, immune cell subsets, and miRNAs in tumor and/or blood and correlate with response.

2.2 Endpoints

2.2.1 Primary Endpoint

- ORR (rate of complete response (CR) + partial response (PR)) per RECIST v1.1

2.2.2 Secondary Endpoints

- Toxicity will be graded according to the National Cancer Institute's Common Terminology Criteria for Adverse Events (NCI-CTCAE) version 4
- ORR (rate of irCR + irPR) per irRC

- PFS per RECIST 1.1 is defined from day 1 of treatment until disease progression or death as a result of any cause, with progression defined per RECIST 1.1
- PFS per irRC is defined from Day 1 of treatment until disease progression or death as a result of any cause, with progression defined per irRC
- OS is defined from Day 1 of treatment until death as a result of any cause

2.2.3 Correlative Endpoints

- PD-L1/2
- Immune cell subsets
- miRNAs

3. ELIGIBILITY CRITERIA

3.1 Inclusion Criteria

Subject must meet all of the following applicable inclusion criteria to participate in this study:

1. Written informed consent and HIPAA authorization for release of personal health information. **NOTE:** HIPAA authorization may be included in the informed consent or obtained separately.
2. Age \geq 18 years at the time of consent.
3. ECOG Performance Status of 0-1 within 28 days prior to registration.
4. Histological or cytological evidence of renal cell carcinoma (initial diagnosis).
5. Metastatic disease.
6. Progressive disease on nivolumab + ipilimumab regimen or nivolumab alone. **NOTE:** Patients who have completed at least one dose of ipilimumab + nivolumab and progress or have completed the 4 doses of ipilimumab + nivolumab and progress during nivolumab monotherapy maintenance are eligible. Patients who have completed at least one dose of nivolumab monotherapy and have progressed are also eligible. Patients who discontinue prior ipilimumab + nivolumab or nivolumab monotherapy for toxicity are excluded.
7. Target lesions according to RECIST v1.1 or non-target bone lesions assessed by bone scan or PET scan.
8. A subject with prior brain metastasis may be considered if they have completed their treatment for brain metastasis at least 4 weeks prior to study registration, have been off corticosteroids for \geq 4 weeks, and are asymptomatic.
9. Prior cancer treatment (excluding nivolumab + ipilimumab or nivolumab alone) must be completed at least 28 days prior to start treatment and the subject must have recovered from all reversible acute toxic effects of the regimen (other than alopecia or neuropathy)

to \leq Grade 1 or baseline. If subject underwent major surgery or radiation therapy of >30 Gy, they must have recovered from the toxicity and/or complications from the intervention.

10. Demonstrate adequate organ function as defined in the table below; all screening labs to be obtained within 28 days prior to registration.

System	Laboratory Value
Hematological	
Platelets	$\geq 100 \times 10^9/L$
Absolute Neutrophil Count (ANC)	$\geq 1.5 \times 10^9/L$
Hemoglobin (Hgb)	$\geq 9 \text{ g/dL}$ or $\geq 5.6 \text{ mmol/L}$
Renal	
Creatinine OR Measured or calculated ¹ creatinine clearance (CrCl) (glomerular filtration rate [GFR] can also be used in place of CrCl)	$\leq 1.5 \times$ the upper limit of normal (ULN) OR $\geq 60 \text{ mL/min}$ for subject with creatinine levels $>1.5 \times$ institutional ULN
¹ Creatinine clearance should be calculated per institutional standard	
Hepatic	
Bilirubin	$\leq 1.5 \times$ ULN OR Direct bilirubin \leq ULN for subjects with total bilirubin levels $> 1.5 \times$ ULN
Aspartate aminotransferase (AST)	$\leq 3 \times$ ULN
Alanine aminotransferase (ALT)	$\leq 3 \times$ ULN
Coagulation	
International Normalized Ratio (INR) or Prothrombin Time (PT) Activated Partial Thromboplastin Time (aPTT)	$\leq 1.5 \times$ ULN unless subject is receiving anticoagulant therapy as long as PT/INR/PTT is within therapeutic range of intended use of anticoagulants

11. Women of childbearing potential (WOCBP) must have a negative serum pregnancy test during screening and a negative urine pregnancy test within 3 days prior to first dose of study drug. If the screening serum test is done within 3 days prior to receiving the first dose of study drug, a urine test is not required.

12. Women of childbearing potential must be willing to abstain from heterosexual intercourse or to use an effective method of contraception from the time of informed consent until 5 months after the last dose of study drug.

13. Men who are sexually active with WOCBP must use any contraceptive method with a failure rate of less than 1% per year. Men receiving study drugs and who are sexually active with WOCBP will be instructed to adhere to contraception for a period of 3 months after the last dose of entinostat.

14. As determined by the enrolling physician or protocol designee, ability of the subject to understand and comply with study procedures for the entire length of the study.

15. Life expectancy of at least 6 months per investigator discretion.

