3: Thyroid function to be checked at screening, Cycle 2 Day 1, Cycle 4 Day 1, then every 3rd cycle thereafter starting with Cycle 6. More frequent testing is at the discretion of the site investigator. TSH will be obtained. T4 and T3 including free versus total testing is at the discretion of the site investigator.

4: For women of childbearing potential (WOCBP): serum pregnancy test during screening and a urine pregnancy test within 3 days prior to first dose of study drugs. If the screening serum test was done within 3 days prior to receiving the first dose of study drugs, a urine test is not required.

5: Tumor response assessment will be performed at screening, prior to Cycle 3 Day 1 then prior to Cycle 5 (±7); Tumor imaging to be performed every 8-12 weeks after Cycle 5 based on investigator discretion. Tumor imaging to be done at treatment discontinuation at discretion of investigator. Baseline bone scan will be obtained if there is any suspicion of metastatic bone involvement. If bone scan is positive at baseline, it will be included with subsequent tumor response assessments as noted above at the discretion of the treating physician. MRI of brain should be performed at screening only to evaluate for the presence of brain metastases. Additional imaging of the brain will be at the discretion of the treating physician. Tumor imaging modality used should be consistent throughout trial.

6: Archival tissue from a metastatic lesion or nephrectomy (metastatic lesion preferred) is required if available and will be obtained at screening. If archival tissue is unavailable, patients will be given the option to consent to a biopsy during the screening phase prior to Cycle 1 Day 1 treatment. All subjects with accessible tumor will be given the option to consent to a second optional biopsy on Cycle 2 Day 1. The Cycle 2 Day 1 samples will be collected ~2 hours following the most recent dose of entinostat. To ensure that these samples are obtained at the correct time, patients are urged to take their entinostat dose in the clinic on the day of on-treatment sample collection. The time of the entinostat dose and the time of sample collection must be recorded.

7: Serial blood samples for PBMCs and plasma, serum will be collected prior to treatment Cycle 1 Day 1, Cycle 2 Day 1, Cycle 4 Day 1, and then every 2nd cycle thereafter starting with Cycle 6.

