9.2 Non-measurable Lesions

All other lesions (or sites of disease), including small lesions (longest diameter <10 mm or pathological lymph nodes with ≥ 10 to <15 mm short axis), are considered non-measurable disease. Bone lesions, leptomeningeal disease, ascites, pleural/pericardial effusions, lymphangitis cutis/pulmonitis, inflammatory breast disease, and abdominal masses (not followed by CT or MRI), are considered as non-measurable.

NOTE: Cystic lesions that meet the criteria for radiographically defined simple cysts should not be considered as malignant lesions (neither measurable nor non-measurable) since they are, by definition, simple cysts. ‘Cystic lesions’ thought to represent cystic metastases can be considered as measurable lesions, if they meet the definition of measurability described above. However, if non-cystic lesions are present in the same subject, these are preferred for selection as target lesions.

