9.5 Evaluation of Target Lesions

Complete Response (CR)	Disappearance of all target lesions. Any pathological lymph nodes (whether target or non-target) must have reduction in short axis to <10 mm.
Partial Response (PR)	At least a 30% decrease in the sum of the diameters of target lesions, taking as reference the baseline sum diameters
Progressive Disease (PD)	At least a 20% increase in the sum of the diameters of target lesions, taking as reference the smallest sum on study (this includes the baseline sum if that is the smallest on study). In addition to the relative increase of 20%, the sum must also demonstrate an absolute increase of at least 5 mm. (Note: the appearance of one or more new lesions is also considered progressions).
Stable Disease (SD)	Neither sufficient shrinkage to qualify for PR nor sufficient increase to qualify for PD, taking as reference the smallest sum diameters while on study

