9.8.3 Objective Response Rate

The objective response rate is the proportion of all subjects with confirmed PR or CR according to RECIST 1.1, from the start of treatment until disease progression/recurrence (taking as reference for progressive disease the smallest measurements recorded since the start of treatment).

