12.3 Sample Size and Accrual

For the safety Lead-In, up to 18 subjects may be enrolled. For Phase II, assuming a type I error rate of 5% and a power of 90% to compare an uninteresting overall response rate (per RECIST 1.1) of 5% while declaring efficacy at 20%, Simon's optimal two stage design enrolls 21 patients in the first stage (with 6 of the 21 from the Safety Lead-in RP2D cohort). If at most one response is seen, then the trial is terminated for futility. Otherwise, stage 2 accrual continues to a total of 41 patients. If at most 4 patients respond among the 41 patients, the combination would not warrant further investigation. If at least 5 patients respond, this therapy would warrant further investigation. The average sample size is 26.66 and the early termination probability is 71.70% for a drug with a response rate of 5%. All the calculations are based on the R function ph2simon from the package clinfun.

Due to Funder decision, enrollment will halt after completion of accrual to the safety lead in group and not move on to Phase II. This decision is a result of a shift in priorities at the Funder level and not due to safety issues. Subjects currently on treatment will continue until the criteria for treatment discontinuation as defined above is met.

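### Patients eligible on bone lesions alone can never have a PR and lack some response categories, yet they count in the ORR denominator

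*Combined protocol and SAP*

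**What the plan says.** Inclusion criterion 7 (section 3.1) asks for "Target lesions according to RECIST v1.1 or non-target bone lesions assessed by bone scan or PET scan". The two routes are alternatives, so a target lesion is not required. Below, bone-only means a patient who qualifies by the second route and has no target lesion.

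Section 9.2 puts "Bone lesions, leptomeningeal disease, ascites, pleural/pericardial effusions" and similar sites among the non-measurable lesions, and 9.3 draws target lesions from measurable lesions only. A PR in 9.5 is "At least a 30% decrease in the sum of the diameters of target lesions", measured against the baseline sum. Section 9.6 gives non-target lesions three categories: CR, non-CR/non-PD and PD.

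On the denominator, 9.8.3 states: "The objective response rate is the proportion of all subjects with confirmed PR or CR according to RECIST 1.1". The Evaluable population in 12.4 needs one dose plus a post-baseline assessment or death, with no condition on measurable disease. Section 12.7.1 analyses all evaluable and eligible patients, and 12.7.2 treats ORR by irRC in the same way.

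On imaging, the calendar in section 7 has a bone-scan row with later time points. Footnote 5 says of a scan that is positive at baseline that "it will be included with subsequent tumor response assessments as noted above at the discretion of the treating physician". PET can qualify a patient but has no calendar row.

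Sections 5.3 and 12.3 say that accrual stops after the safety lead-in and that Phase II will not be run.

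**The concern.** ORR per RECIST 1.1 is the only primary endpoint listed in 2.2.1, and PR is one of its two components. A bone-only patient enters the denominator but can reach the numerator only if all disease disappears and that is confirmed at least four weeks later (9.8.2). Confirmation needs repeat bone imaging, which footnote 5 does not guarantee.

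Two things follow. First, the reported ORR mixes patients who can have a PR with patients who cannot, in proportions set by who happened to enrol. Second, some of these patients cannot be classified from the rules as written, so whoever prepares the tables must improvise. With about six patients at the RP2D, one such decision visibly moves the result, and it should not be made after responses are known.

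**Working it through.** **Classification of a patient with no target lesion**

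| Rule | Outcome |
|---|---|
| PR, 9.5 and 9.7 | Impossible: there is no baseline sum, and every PR row in 9.7 needs a target status of CR or PR |
| CR, 9.6 | Defined for non-target lesions, but 9.7 has no matching overall-response row |
| Non-CR/non-PD, 9.6 | Defined, but 9.7 has no matching row |
| PD, 9.7 | Works: two rows assign PD whatever the target status |
| irCR, 9.9.4 | Works in words: disappearance of all lesions, index and non-index |
| irPR, 9.9.2 to 9.9.4 | Needs a 50% fall from a baseline index SPD of 0, so it cannot be computed |
| irSD, 9.9.4 | Residual category, so it can be assigned |
| irPD, 9.9.3 and 9.9.4 | Needs a 25% rise: 0/0 with no lesions to measure, division by zero once a new measurable lesion appears. Growth of non-index lesions alone does not count |

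**The plan's own design figures (12.3)**

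Inputs: p0 = 0.05, p1 = 0.20; stage 1 of 21 patients, stopping at 1 response or fewer; 41 in total, success at 5 or more.

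- P(stop at stage 1) = (1−p)^21 + 21p(1−p)^20. At p = 0.05: 0.3406 + 0.3764 = 0.7170, as stated (71.70%).
- Expected size = 21 + 20 × (1 − 0.7170) = 26.66, as stated.
- P(declare efficacy) = Σ over x = 2 to 21 of P(X1 = x) × P(X2 ≥ 5 − x), with X1 ~ Bin(21, p) and X2 ~ Bin(20, p). This gives 0.0457 at p = 0.05 and 0.9017 at p = 0.20, within the stated 5% and 90%.

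The design figures are correct.

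**Dilution of the planned Phase II test**

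Let f be the bone-only share and c their CR rate. Both are assumptions; the documents give neither. With a true ORR of 20% in patients with target lesions, ORR in all patients = 0.20 × (1 − f) + c × f. The type I error column uses 0.05 × (1 − f), that is, c = 0 under the null.

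| f | c | ORR, all patients | Power | P(stop at stage 1) | Type I error |
|---|---|---|---|---|---|
| 0 | – | 0.20 | 0.9017 | 0.0576 | 0.0457 |
| 10% | 0 | 0.18 | 0.8438 | 0.0869 | 0.0312 |
| 20% | 0 | 0.16 | 0.7605 | 0.1285 | 0.0200 |
| 10% | 5% | 0.185 | 0.8604 | | |
| 20% | 5% | 0.17 | 0.8056 | | |

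**The lead-in cohort of 6**

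Assume 20% ORR in patients with target lesions and no response in bone-only patients. With k bone-only patients, expected ORR = 0.20 × (6 − k)/6 and P(at least one response) = 1 − 0.8^(6−k).

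| k | Expected ORR | P(at least one response) |
|---|---|---|
| 0 | 20.0% | 0.738 |
| 1 | 16.7% | 0.672 |
| 2 | 13.3% | 0.590 |

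**The case against.** The strongest reply is that little now depends on this. Phase II is cancelled, 12.7.1 is worded for Phase II, and the lead-in's decision is the RP2D by DLT count, which measurability does not touch. An ORR in all subjects is also a legitimate, conservative estimand for the population the trial admits. All of this stands. It removes the power loss as a live problem and lowers the priority. It does not settle how a bone-only patient is to be classified when lead-in responses are reported, and 13.5 requires results for primary and secondary objectives to be posted.

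A reader might infer more than the documents support:

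- That bone-only patients cannot respond, so that one of them caps a six-patient ORR at 5/6. Section 9.6 allows a non-target CR, so 5/6 is not a cap.
- That ORR is biased downward as a matter of fact. The effect is zero if no such patient was enrolled, and it exists only relative to patients with measurable disease.
- That the 5% and 20% planning rates presuppose measurable disease. Section 12.3 does not say so.
- That progression cannot be recorded, or that irRC fails altogether. The 9.7 table assigns PD regardless of target status, and irCR and irSD remain usable.
- That bone disease will go unimaged. The calendar schedules bone scans, and footnote 5 asks for a consistent modality throughout. The difficulty is that the same footnote makes the repeat discretionary.

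**Conclusion.** The point holds as a gap in the response rules and the ORR denominator, worth correcting before lead-in results are tabulated. It does not invalidate the design. By the protocol's own definitions a bone-only patient cannot have a PR, has no CR or non-CR/non-PD row in 9.7, has no computable irPR or percentage-based irPD, and still counts in ORR.

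Any dilution is conservative: with no bone-only responses, type I error falls from 4.57% to 3.12% at a 10% share, so it cannot manufacture a finding of efficacy. For the planned Phase II alone, power would have fallen from 90.2% to 84.4% at an assumed 10% share and to about 76% at 20%, or to 86.0% and 80.6% if 5% of bone-only patients had a CR. What still matters is the lead-in ORR, where one non-responding bone-only patient among six moves the expected value by 3.3 percentage points. These sizes rest on an assumed share, an assumed 20% ORR in patients with target lesions, and the assumed CR rates shown.

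**What to change.** 1. In 9.8.3, 12.7.1 and 12.7.2, state that RECIST and irRC ORR will be reported in treated patients with at least one baseline target or index lesion, alongside ORR in all treated patients, with the number and outcomes of bone-only patients listed.
2. Add rows to 9.7 for patients with non-target disease only: CR, non-CR/non-PD and PD.
3. Reconcile footnote 5, which leaves repeat bone scans to discretion, with the calendar's bone-scan row and with the use of bone lesions as the sole qualifying disease.

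These are wording changes that leave eligibility for the DLT question alone. The costs are a smaller denominator for the measurable-disease ORR and an exclusion defined after enrolment. Because that exclusion removes likely non-responders, it can raise the rate, so the all-treated figure must be shown beside it.

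If enrolment were ever reopened, obtaining 41 patients with target lesions would need 41/0.90 = 45.6, about 46 enrolled at an assumed 10% share (41/0.80 = 51.25, so 52, at 20%), unless Inclusion 7 were changed to require a target lesion.

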3.2 Exclusion Criteria

Subjects meeting any of the criteria below may not participate in the study:

1. History or current evidence of any condition, therapy, or laboratory abnormality that might confound the results of the study, interfere with the subject's participation for the full duration of the study, or is not in the best interest of the subject to participate, in the opinion of the treating investigator, including, but not limited to:
 - Myocardial infarction or arterial thromboembolic events within 6 months prior to screening or severe or unstable angina, New York Heart Association (NYHA) Class III or IV disease, or a QTc interval > 470 msec.
 - Uncontrolled hypertension or diabetes mellitus.
 - Another known malignancy that is progressing or requires active treatment.
 - Any prior history of other cancer within the prior 5 years with the exception of adequately treated basal cell carcinoma or cervical intraepithelial neoplasia [CIN]/cervical carcinoma in situ or melanoma in situ).
 - Active infection requiring systemic therapy.
 - Known active central nervous system (CNS) metastases and/or carcinomatous meningitis.
2. Pregnant or breastfeeding. **NOTE:** breast milk cannot be stored for future use while the mother is being treated on study.
3. Any contraindication to oral agents or significant nausea and vomiting, malabsorption, or significant small bowel resection that, in the opinion of the investigator, would preclude adequate absorption.
4. Allergy to benzamide or inactive components of entinostat.
5. Hypersensitivity to nivolumab, ipilimumab, or any of their excipients.
6. Treatment with any investigational drug or device within 4 weeks prior to registration.
7. Treatment with systemic steroids within 4 weeks prior to registration. **NOTE:** adrenal replacement doses of steroids (equivalent of prednisone 10mg daily) are permitted.
8. Evidence of active autoimmune disease requiring systemic treatment within the past 90 days or a documented history of clinically severe autoimmune disease, or a syndrome that requires systemic steroids or immunosuppressive agents. Subjects with vitiligo or resolved childhood asthma/atopy would be an exception to this rule. Subjects that require intermittent use of bronchodilators or local steroid injections would not be excluded from the study. Subjects with hypothyroidism stable on hormone replacement or Sjogren's syndrome will not be excluded from the study.
9. Interstitial lung disease or history of pneumonitis requiring treatment with corticosteroids.

10. Diagnosis of immunodeficiency; or is receiving chronic systemic corticosteroid therapy or other immunosuppressive therapy (excludes inhaled corticosteroids) within 4 weeks prior to registration.
11. Known history of human immunodeficiency virus (HIV) (HIV 1/2 antibodies). Testing during screening is not required.
12. Known active hepatitis B (e.g., hepatitis B surface antigen-reactive) or hepatitis C (e.g., hepatitis C virus ribonucleic acid [qualitative]). Subjects with past hepatitis B virus (HBV) infection or resolved HBV infection (defined as the presence of hepatitis B core antibody [HBc Ab] and absence of HBsAg) are eligible. HBV DNA test must be performed in these subjects prior to study treatment, and results must be negative to be eligible. Subjects with a history of hepatitis C must be tested for presence of hepatitis C virus (HCV) antibody. If HCV antibody positive, subjects will only be eligible if polymerase chain reaction is negative for HCV RNA.
13. Has received a live vaccine within 30 days prior to planned start of study therapy. Note: Seasonal influenza vaccines for injection are generally inactivated flu vaccines and are allowed; however, intranasal influenza vaccines (e.g., Flu-Mist®) are live attenuated vaccines, and are not allowed.

